1. ACRONYMS AND DEFINITION OF TERMS

Acronym	Meaning		
AE	Adverse Event		
ADSUS	Adult Service Use Schedule		
ANCOVA	Analysis of Covariance		
ANNSERS	The Antipsychotic Non-Neurological Side Effects Scale		
AR	Adverse Reaction		
BARS	Brief Adherence Rating Scale		
BPD	Borderline Personality Disorder		
BPRS	Brief Psychiatric Rating Scale		
CACE	Complier Average Causal Effect		
CI	Chief Investigator		
CONSORT	Consolidated Standards of Reporting Trials		
CRF	Case Report Form		
СТІМР	Clinical Trial of Investigational Medicinal Product		
СТU	Clinical Trials Unit		
DMC	Data Monitoring Committee		
Ecrf	Electronic Case Report Form		
EDC	Electronic Data Capture		
GCP	Good Clinical Practice		
GLM	Generalised Linear Model		
НЕАР	Health Economics Analysis Plan		
IMP	Investigational Medicinal Product		
IPDE	International Personality Disorder Examination		
ITT	Intention to Treat		
MAR	Missing at Random		
MCAR	Missing Completely at Random		
MNAR	Missing Not at Random		
MHRA	Medicines and Healthcare Products Regulatory Agency		

Mitt	Modified Intention to Treat		
MOAS	Modified Overt Aggression Scale		
NHS	National Health Service		
NIHR	National Institute for Health Research		
NWORTH	North Wales Organisation for Randomised Trials in Health		
REC	Research Ethics Committee		
SAE	Serious Adverse Event		
SAP	Statistical Analysis Plan		
SAR	Serious Adverse Reaction		
SASPD	Standardised Assessment of Severity of Personality Disorder		
SCID-II	Structured Clinical Interview for Axis II		
SD	Standard Deviation		
SOP	Standard Operating Procedure		
SUSAR	Suspected Unexpected Serious Adverse Reaction		
TMG	Trial Management Group		
TSC	Trial Steering Committee		
ZAN-BPD	Zanarini Rating Scale For Borderline Personality Disorder		

2. STATISTICAL ANALYSIS PLAN AUTHORSHIP

This SAP has been authored by [name] (Senior Statistician NWORTH CTU), Trial Statistician for the CALMED Trial, with input from [name], Senior Trial Statistician for the trial (Principal Statistician NWORTH CTU), [name] (Chief Investigator) and [name] (Trial Manager).

The study began recruitment in September 2019 however, due to several difficulties such as recruiting in this population and the impacts of COVID-19, which are still ongoing, the study struggled to reach recruitment targets. Efforts were made to increase recruitment to the study but unfortunately recruitment to the study remained an issue.

The sample size of the study was re-calculated and reduced, see section 4.1, however in March 2021, with agreement from independent committees and the funder, the study was terminated. At the time of termination, a final sample of 29 randomised patients was reached.

This document details the planned analysis according to the protocol, given the full sample, and the analysis that will be carried out for the study given the sample reached. It should be noted that the sample is very small, and far below the statistical power required to evaluate the intended research question. Therefore, all results presented following the analysis should be interpreted with caution.

3. INTRODUCTION

3.1 BACKGROUND AND DESIGN

Inpatients with severe borderline personality disorder experience high levels of emotional distress which may be accompanied by high levels of self-harming and aggressive behaviour. Open label studies of treating inpatients with clozapine show major improvements in mental health and reductions in self-harming behaviour. However, to date there are no published or on-going clinical trials of clozapine for people with borderline personality disorder. While clozapine has the potential to generate considerable savings for the NHS, the true risks and benefits of treating people with clozapine are unknown. The CALMED trial is a fully powered two-arm, double-blind, placebo-controlled randomised trial which is designed to establish the clinical effectiveness and cost effectiveness of clozapine for inpatients with severe borderline personality disorder.

Design & Methodology

A two-arm, parallel-group, placebo-controlled trial with an internal pilot and an integrated economic evaluation. The study is funded by the National Institute of Health Research (NIHR) Health Technology Assessment programme. Study groups are standard care plus clozapine, titrated up to a maximum dose of 400mg daily, versus standard care plus an inert placebo. Standard care will include access to psychological interventions, occupational activities and nursing care that are provided to inpatients with BPD.

222 inpatients with BPD will be recruited from seven centres in England over a 24-month period. All participants will be followed-up at three and six months using a battery of assessment scales to measure mental health (Zanarini rating scale for Borderline Personality Disorder - ZAN-BPD, and the Brief Psychiatric rating Scale - BPRS), incidence of violence to self or others (MOAS), acts of deliberate self-harm, health-related quality of life (EQ-5D-3L), side effects of treatment, adherence and adverse reactions. Resource use and costs will be assessed using a modified version of the Adult Service Use Schedule and with nationally available unit costs. We will continue to collect economic data from clinical records on use and type of inpatient treatment, use of community services and quantity and type of medication that participants take throughout the study. We will use a flexible dosing regimen of clozapine. Dosing will start with 12.5 mg once daily and be titrated to 300mg over a 15-day period. Study participants may be prescribed a dose of up to 400mg of clozapine daily, depending on clinical response, patient preference and side effects. The dose may be

maintained at or reduced to a lower dose at any time. Equivalent numbers of placebo capsules will be administered to participants in the control arm of the trial. All those taking part in the study will continue to receive all other treatments as usual.

The trial will involve two linked phases:

Phase 1 - An internal pilot in which participants will be recruited from all centres over a sixmonth period. Data from the internal pilot will be presented to the Trial Steering Committee (TSC) indexed against a priori stop/go criteria, that will be used to determine if the study progresses to phase 2.

Phase 2 - Full trial across all sites over a further 18-month period.

Progression criteria will be assessed at six months according to the following three parameters:

- Number of participants randomised in the first six months. Our target is 55. If above 42 (75% of the target) recruitment would continue. If between 35 and 41 we would discuss continuation with the independent committees and funder. If below 32 (less than 60% of the target) we would stop. Mitigating circumstances for under-recruitment such as a delay in opening one or more of the pilot sites will be discussed with the TSC and may result in an adjustment to the participant target or pilot period.
- At least 75% of the participants recruited to the active arm of the trial in the first three months of the pilot phase of the trial will have started study medication within four weeks of randomisation.
- Three-month follow-up data will have been collected from >70% of those randomised during the first three months of the pilot study.

3.2 TRIAL OBJECTIVES

Primary Objective:

For people receiving inpatient treatment for severe borderline personality disorder who have not made an adequate clinical response despite receiving usual care (including at least three months taking another antipsychotic drug), does the addition of clozapine to their usual care lead to improved mental health six months later, compared to adding an inert placebo to their usual care?

Secondary Objectives:

i) For people receiving inpatient treatment for borderline personality disorder who have not made an adequate clinical response to usual care, does the addition of clozapine lead to greater improvements in health-related quality of life, greater reductions in aggression, suicidal behaviour, and use of services compared to adding a placebo?

ii) For people receiving inpatient treatment for borderline personality disorder who have not made an adequate clinical response to usual care, does the addition of clozapine provide a cost-effective treatment compared to the addition of a placebo?

3.3 CONSORT DIAGRAM

CONSORT 2010 Flow Diagram

Figure 1: CALMED study Flow Chart for CONSORT figures

CONSORT Flow Diagram CALMED Trial v1 10.05.2021

Reasons for Ineligibility

Inclusion criteria:

- Aged 18 years or over
- o Currently an inpatient on a mental health unit
- Meeting DSM-IV diagnostic criteria for borderline personality disorder
- Failure to make an adequate clinical response to taking antipsychotic medication other than clozapine for at least three months
- o Have a satisfactory pre-treatment full blood count
- Have had their weight and blood glucose recoded in their clinical records
- Has severe personality disorder

Exclusion criteria:

- o Current clinical diagnosis of schizophrenia or bipolar I disorder
- Prescribed clozapine within the previous two weeks
- Is pregnant or trying to conceive, breastfeeding, or a woman of childbearing potential not using a highly effective birth control.
- o Contraindications to clozapine
- Due to be discharged from the unit within the following two weeks and it is not possible to continue the necessary monitoring of physical health as an outpatient
- Unable to speak sufficient English to complete the baseline assessment
- Unwilling or unable to provide written informed consent to take part in the study
- unable to undertake regular blood tests

Figure 1: List of reasons for ineligibility

Figure 2: CALMED study Flow Chart for CONSORT figures - figure references

Reasons patient declined

- Does not want to be randomised / risk placebo
- Does not want to take study medication
- Does not want to complete questionnaires/interviews
- Does not want to have blood tests
- Other

Figure 2: List of reasons for patient declining participation

Reasons for post-consent withdrawal

- Protocol Deviation
- Adverse Event
- Death
- Withdrawal of Consent
- Lost to Follow Up
- Trial terminated by sponsor
- Other

Figure 3: List of reasons for post-consent withdrawal

4. STATISTICAL CONSIDERATIONS

4.1 SAMPLE SIZE JUSTIFICATION

The sample size calculation for the study was based on the primary hypothesis that, for inpatients with borderline personality disorder, the addition of clozapine to usual treatment reduces symptoms of the disorder measured at six months (standard deviation 7.89) using the Zanarini Rating scale for Borderline Personality Disorder (ZAN-BPD). 166 participants (83 receiving clozapine and 83 receiving placebo) will need to be randomised to have 90% power to detect a four point clinically important difference in ZAN-BPD score at six months, using a 0.05 level of statistical significance. To take account of 25% loss to follow-up we planned to recruit 222 subjects. We will seek to further increase the sample size to ensure that we have data on 166 participants who took at least one dose of trial medication.

The above original sample size estimate was calculated with a two-sample t-test method, this is used with the understanding that the model used for analysis (i.e. ANCOVA) will have higher statistical power which is seen as a conservative approach and often adopted to power studies when there is little additional data available. An alternative approach would be to use an ANCOVA model calculation. This method requires an additional assumption of the correlation covariate for the calculation, which there is often no robust data available for, thus reducing the certainty in the sample size proposed. However, based on ZAN-BPD data held by the study team and available in the literature we felt confident to estimate the correlation co-efficient for the current study. Some caution is still being applied by taking the most conservative estimate of those available.

Using data from a previous trial (Labile) and the current CALMED data the correlations were calculated were between 0.2 and 0.4. Walters et. al. (2019) found in most cases the correlation between baseline and follow up assessments was between 0.4 and 0.6. It is possible that a correlation of 0.4 could be seen; however, assuming the correlation to be higher than it is would reduce the potential power of the final analysis. Therefore, we propose to take a more conservative approach and use an estimate of 0.3.

It was recommended that the trial aims to recruit, for analysis, a sample of N=118. Which, with a 0.3 correlation of baseline and follow-up scores, would give 90% power to detect a 4.0 difference on the ZAN-BPD scale with a 7.89 SD at a 5% significance level.

By adopting this alternative method of sample size estimation additional information can be taken into account ultimately relating the sample more closely to the analysis method that will be used. A benefit of this alternate is that all original parameters will remain the same (mean difference of 4.0 and assumed standard deviation of 7.89) thus preserving the primary research aim.

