4.3 LEVELS OF CONFIDENCE AND P-VALUES

All statistical tests for the primary endpoints will be two-sided and will be performed using a 5% significance level. Confidence intervals for estimated effects will be presented as 95% and two-sided. As this study will not provide conclusive evidence and will lack statistical power, secondary outcomes will not be adjusted for multiple comparisons. Results will be interpreted with caution, 95% confidence intervals will be reported alongside any p-value or effect.

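### SAP section 4.1: 118 analysed gives about 82% power at a baseline to follow-up correlation of 0.3, not the stated 90%, which needs about 152

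*SAP*

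**What the plan says.** Section 4.1 first gives a two-sample t-test calculation: 166 participants (83 per arm) for 90% power to detect a four-point difference in ZAN-BPD at six months with SD 7.89, raised to 222 for 25% loss. It then moves to an ANCOVA calculation that uses the correlation between baseline and follow-up scores.

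On the choice of correlation it says "Some caution is still being applied by taking the most conservative estimate of those available". It reports that, in a previous trial and the current data, "the correlations were calculated were between 0.2 and 0.4", and it settles on 0.3.

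The result is: "It was recommended that the trial aims to recruit, for analysis, a sample of N=118". The power attached to it is: "Which, with a 0.3 correlation of baseline and follow-up scores, would give 90% power to detect a 4.0 difference on the ZAN-BPD scale". The same sentence gives the SD as 7.89 and the significance level as 5%. The section adds that "all original parameters will remain the same (mean difference of 4.0 and assumed standard deviation of 7.89").

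Section 4.3 fixes the sidedness: "All statistical tests for the primary endpoints will be two-sided and will be performed using a 5% significance level".

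**The concern.** Adjusting for a baseline covariate whose correlation with the outcome is r multiplies the residual variance by 1 − r². At r = 0.3 that is a 9% reduction, so the required number should fall by about 9% from 166. The SAP's number falls by 29% (118/166 = 0.71). A reduction of that size needs a much stronger correlation than the SAP assumes or reports.

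What is at stake is the record of why the target was reduced. Section 4.1 presents 118 as holding the original 90% power. If it does not, the chance of missing a true four-point difference at that size is about 18% and not 10%. A report, or a later trial in this population, that repeated the calculation would repeat the error.

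A smaller problem lies in the same paragraphs. The value 0.3 is introduced as the most conservative estimate available, but the observed range starts at 0.2.

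**Working it through.** **Inputs.** All come from the SAP:
- difference 4.0, SD 7.89, power 90%, 5% level, correlation 0.3 and observed range 0.2 to 0.4 (section 4.1);
- two-sided test (section 4.3);
- equal arms, taken from the original 83 and 83 (section 4.1).

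**Formulas.** With n per arm and residual SD s, the noncentrality parameter is δ = 4.0 / (s × √(2/n)). Power is the probability that a noncentral t with parameter δ falls beyond the two-sided 5% critical value. Degrees of freedom are 2n − 2 for the t-test and 2n − 3 for ANCOVA with one covariate. For ANCOVA, s = 7.89 × √(1 − r²).

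**Step 1: the original figure.** With s = 7.89 and n = 83, δ = 3.27 and power is 90.1%. With n = 82 it is 89.7%. So 83 per arm is the smallest size that reaches 90%, and 166/0.75 = 221.3, rounded up to 222. Both of the SAP's original figures reproduce.

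**Step 2: the revised figure at r = 0.3.** Here s = 7.89 × √0.91 = 7.53. With n = 59 (118 in total), δ = 2.89 and power is 81.7%. A normal approximation gives 82.3%. Power first reaches 90% at n = 76 (90.2%; n = 75 gives 89.9%), so 152 in total. The normal approximation gives 150.

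**Step 3: the SAP's own range of correlations.**

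| r | Residual SD | Power at 118 analysed | Analysed for 90% power |
|---|---|---|---|
| 0.2 | 7.73 | 79.6% | 160 |
| 0.3 | 7.53 | 81.7% | 152 |
| 0.4 | 7.23 | 84.6% | 140 |

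No correlation in the range gives 90% at 118. Even r = 0.5 gives only 88.4%.

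**Step 4: where 118 may come from.** If 0.3 is used as R², then s = 7.89 × √0.7 = 6.60. With n = 59, δ = 3.29 and power is 90.4%; with n = 58 it is 89.9%. The smallest size that reaches 90% is therefore exactly 59 per arm, or 118. The implied correlation is √0.3 = 0.55.

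**Step 5: other readings of 118.**
- One-sided 5% test at r = 0.3: 122 to 124 needed, with 89.0% to 89.3% power at 118. This comes close, but section 4.3 specifies two-sided tests and the original 166 is two-sided.
- Change-score analysis: 230 needed.
- 118 per arm: 98% power.
- 118 before 25% loss: about 71% power.
- ANCOVA on the mean of two follow-ups: gives 118 only if the two follow-ups are assumed to correlate at 0.6. The SAP does not state this, and the primary outcome is at six months only.
- r = 0.2 with 80% power, normal approximation: also gives 118, but contradicts both the stated 0.3 and the stated 90%.

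**The case against.** The strongest objection is that the error has little consequence. Section 2 of the SAP says that the trial was terminated with 29 randomised and that this is far below the power required. Sections 4.3, 6.7 and 6.10 repeat the caution. No model, analysis set, missing-data rule or test depends on 118. At 14 per arm (28 in total, the nearest equal split) and r = 0.3, power is about 27%, so the trial is underpowered whichever target is used. This stands, and it limits the point to a correction of what is reported.

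Three stronger readings are tempting, and the document does not support them.

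- A reader might infer that the statement about unchanged original parameters is false. It is not: the SAP names those parameters as the 4.0 difference and the 7.89 SD, and both are unchanged. What fails is the link between 118, the correlation of 0.3 and 90% power.
- A reader might take it as established that 0.3 was entered as R-squared. The exact match is strong evidence, but the SAP gives no formula or software input, so this remains an inference. The power is wrong as stated whatever the cause.
- A reader might infer that the final report will carry a false power statement. That report is not at hand, and section 6.7 already says that the study will not be statistically powered.

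On the choice of 0.3, the SAP also describes it as more conservative than 0.4, which is accurate. Only the claim that it is the most conservative available conflicts with the reported range.

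**Conclusion.** The concern holds as a reporting error. On the SAP's own inputs, 118 analysed gives about 82% power and not 90%, and about 152 analysed are needed for 90%, a shortfall of 34. Over the observed correlations of 0.2 to 0.4, 118 gives about 80% to 85%. The gap is too large for rounding or for the choice between normal and t calculations, which differ by less than one percentage point of power and by two participants.

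The result assumes equal arms, a two-sided 5% test and ANCOVA with the baseline score as the only covariate. The first two are in the SAP; the third is the natural reading of the ANCOVA calculation that it describes. The conclusion does not depend on how the figure arose. Nothing in the planned analysis of the 29 randomised participants is affected.

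**What to change.** Keep 118 in section 4.1, because the sentence records what was recommended and replacing the number would misstate that history. Correct the power attached to it. The corrected text should say that the recommended sample was 118 for analysis; that, with a correlation of 0.3 between baseline and six-month scores, a difference of 4.0, SD 7.89 and a two-sided 5% test, this gives about 82% power; and that about 152 analysed would be needed for 90%. Make the same correction in any report that repeats the calculation.

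If the sponsor's calculation files confirm that 0.3 was entered as R-squared, say so, and note that the implied correlation of about 0.55 lies above the observed 0.2 to 0.4.

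Delete the wording that 0.3 is the most conservative estimate available, or show the results at 0.2 beside it: about 80% power at 118, and 160 analysed for 90%. The sentence on the unchanged difference and SD can stay.

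The cost is a few sentences in the SAP and in any report that repeats them. Recruitment is closed, so no participants are involved and no analysis is rerun. The stated power becomes less favourable.

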4.2 RANDOMISATION

Randomisation was via a secure online system using a sequentially randomised dynamic adaptive algorithm stratified by centre (list), ward type (general adult, low secure, medium secure and high secure) and gender (male or female), hosted by NWORTH, Bangor university. Within the algorithm, the likelihood of the participant being allocated to each treatment group is recalculated based on the participants already recruited and allocated (Russell et. al., 2011). This recalculation is done at the overall allocation level, within stratification variables and within stratum level (the relevant combination of stratification levels). By undertaking this recalculation, the algorithm ensures that balance is maintained within acceptable limits of the assigned allocation ratio while maintaining unpredictability.

Randomisation creates a unique randomisation code for the participant. A trial prescription form will then be completed by the local investigator. This will be sent to the pharmacy that will dispense the trial medication to the ward where the participant is being treated.

4.3 LEVELS OF CONFIDENCE AND P-VALUES

All statistical tests for the primary endpoints will be two-sided and will be performed using a 5% significance level. Confidence intervals for estimated effects will be presented as 95% and two-sided. As this study will not provide conclusive evidence and will lack statistical power, secondary outcomes will not be adjusted for multiple comparisons. Results will be interpreted with caution, 95% confidence intervals will be reported alongside any p-value or effect.

4.4 ADHERENCE AND COMPLIANCE

The planed analysis for Trial Adherence was to investigate the effect of treatment adherence using complier average causal effect (CACE) estimation methods. Intention To Treat (ITT) analysis does not represent treatment effect under non-compliance of treatment, we therefore planned to use CACE analysis to explore whether treatment effect is directly affected by the level of compliance. However, due to the small sample size the above analysis is not appropriate, therefore, compliance and adherence will be reported descriptively as both a dichotomous and continuous variable. The dichotomous: whether the participant took medication at a dose of 100mg or more without interruption during the six months prior to the final follow-up interview; b) Continuous - percentage of medication the participant took in the month prior to competing the six month follow up assessment using data from the Brief Adherence Rating Scale.

This will be presented overall and split by treatment group, continuous variables will be reported with mean values, standard deviations and ranges. Categorical variables will be presented with counts and percentages.

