4.8 ANALYSIS SETS

All primary analysis will be using modified ITT analysis (mITT), in which all randomised participants will be included who have taken at least one dose of trial medication.

For participants that were randomised but did not take any trial medication, they will be included in summary descriptive statistics only as they are not part of the mITT dataset (see figure 1).

A per protocol analysis set will also be used. This will consist of participants who took trial medication, at least until the first follow-up at 3 months. i.e. all those in the mITT set who withdrew from trial medication prior to their 3 month follow up are removed in addition to the participants randomised that didn't take trial medication at all.

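### SAP section 4.4: the yes/no adherence window takes in the scheduled titration, so a participant who follows the schedule and is interviewed on time is classed as non-adherent

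*SAP*

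**What the plan says.** Section 4.4 drops the planned CACE analysis because of the small sample and reports adherence descriptively instead, overall and by arm, in two forms. The dichotomous form is "whether the participant took medication at a dose of 100mg or more without interruption during the six months prior to the final follow-up interview". The continuous form is the BARS percentage for the month before the six-month assessment.

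Section 3.1 sets the schedule that this definition has to fit:

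- Follow-up: "All participants will be followed-up at three and six months using a battery of assessment scales". After six months, Table 2 lists only the service-use schedule.
- Dosing: "Dosing will start with 12.5 mg once daily and be titrated to 300mg over a 15-day period".
- Flexibility: the dose may be "maintained at or reduced to a lower dose at any time".
- Control arm: "Equivalent numbers of placebo capsules will be administered to participants in the control arm of the trial".

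The primary objective in section 3.2 asks whether adding clozapine will "lead to improved mental health six months later, compared to adding an inert placebo to their usual care". No section exempts the titration days from the adherence definition or starts its window later.

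**The concern.** The look-back is as long as the follow-up. If the interview falls six months after randomisation or first dose, the window reaches back to the start of treatment, when the schedule itself sets the dose below 100 mg. A participant who takes every capsule as prescribed is then recorded as non-adherent.

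With CACE dropped, this is one of two adherence summaries that section 4.4 keeps, and the only one of the two that covers more than the last month. Applied as written, it would show almost no adherence in either arm. Any participants who did qualify would do so because they were interviewed late. If the analyst quietly relaxed the rule to get a usable figure, the reported variable would no longer be the pre-specified one.

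**Working it through.** The SAP states no figure to reproduce here. The check is a day count.

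**Inputs from the SAP**
- Threshold of 100 mg, without interruption, over six months (section 4.4).
- 12.5 mg at the start, rising to 300 mg over 15 days (section 3.1).
- Last interview at six months (section 3.1 and Table 2). Table 3 agrees: last recruitment January 2021, final visit July 2021.

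**Assumptions**
- Six months = 183 days.
- Day 1 is 12.5 mg and day 15 is 300 mg. The steps between are not given, so two paths and the outer bounds are shown.
- Delay from randomisation to first dose: 0 days, or 28 days as an illustration. The second value is taken from the pilot progression criterion ("will have started study medication within four weeks of randomisation"), which is not a maximum.

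**Days below 100 mg during titration**
- Linear: dose on day d = 12.5 + 287.5 × (d − 1)/14. Day 5 gives 94.6 mg and day 6 gives 115.2 mg, so 5 days are below.
- Geometric: dose on day d = 12.5 × 24^((d − 1)/14). Day 10 gives 96.4 mg and day 11 gives 121.0 mg, so 10 days are below.
- Outer bounds: 1 day (100 mg reached on day 2) to 14 days (reached only on day 15).

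**Largest share of the window that can qualify** = (183 − delay − days below 100 mg)/183, with six months counted from randomisation and the interview on time.

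| Titration path | No delay | 28-day delay |
|---|---|---|
| 1 day below | 182/183 = 99% | 154/183 = 84% |
| Linear, 5 days below | 178/183 = 97% | 150/183 = 82% |
| Geometric, 10 days below | 173/183 = 95% | 145/183 = 79% |
| 14 days below | 169/183 = 92% | 141/183 = 77% |

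The rule needs 100%, and no cell reaches it. For a participant to qualify, the interview must be late by at least the delay plus the days below 100 mg: 1 to 14 days with no delay, and 29 to 42 days with a 28-day delay.

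**Anchor.** If six months is counted from the first dose, the delay drops out and the no-delay column applies. The criterion still fails on day 1, at 12.5 mg.

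**Arms.** The SAP does not say how the 100 mg threshold is read for placebo. If it is read through the matched capsule numbers, the control arm fails in the same way.

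**The case against.** The strongest reply is that the authors probably meant no interruption once 100 mg had been reached, and that visit windows, which section 4.5 places in the protocol, could let some interviews fall late enough. Both are possible. But the text gives no such start to the window, and qualifying through a late visit is itself a fault in an adherence measure.

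A second reply is that little depends on this variable, and that stands. It enters no model. Readers would still have BARS at three and six months, treatment discontinuation with reasons (section 6.5), withdrawal of medication for adverse effects (section 5.2) and the per-protocol analysis (section 6.10). Section 2 already says that the sample is far below the required power, so the reading of a null result does not turn on this variable.

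A reader might also infer more than the SAP supports:

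- **That no participant can ever qualify, or that the count must be 0 of 29.** This needs every interview to be on time and an anchor that the SAP does not state. The denominator is also wrong: 29 is the number randomised. Section 4.8 allows for participants who were never dosed and who would rightly count as non-adherent. Section 4.6 reports 18% of the primary outcome missing, and a participant with no final interview has no window to assess.
- **That four weeks is the longest permitted delay.** It belongs to a pilot criterion requiring at least 75% of early active-arm recruits to have started by then, so later starts are compatible with it.
- **That the definition contradicts the per-protocol set**, described as "participants who took trial medication, at least until the first follow-up at 3 months". That set serves a different purpose and need not match.
- **That allowing dose reductions contradicts the 100 mg threshold.** Classing a reduced dose as below threshold is a legitimate choice of definition; it only needs to be stated.

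**Conclusion.** The concern holds in a limited form. As written, sections 3.1 and 4.4 conflict: a participant who follows the schedule and is interviewed at six months is non-adherent by definition. The shortfall is 1 to 14 days of a 183-day window if dosing starts at randomisation, and more if the first dose is delayed and six months runs from randomisation. The reported rate would be near 0% in both arms or would partly reflect how late interviews were held.

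This rests on a literal reading, on six months counted from randomisation or first dose, and on interviews close to six months. The exact number of days depends on titration steps that the SAP does not give, but the conclusion does not, because the first day's dose is below the threshold on any path. The primary analysis, the per-protocol set and the BARS measure are unaffected.

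**What to change.** Reconcile sections 3.1 and 4.4 by rewording the dichotomous definition:

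1. Start the adherence window after the scheduled titration period and end it at the 6-month interview.
2. State the day from which titration is counted. Counted from randomisation, a participant whose first dose came 28 days later would still fail. Counted from the actual first dose, that participant would not.
3. State how permitted dose reductions are classed, and how the threshold is read for placebo capsules.
4. State how never-dosed participants and those without a final interview are handled.

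No change of dose, threshold or schedule is implied. The cost is a few lines of SAP wording, best settled before the data are analysed. The SAP does not name the data source for this variable, so the authors should confirm that dated dose records exist to support the chosen window.
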